## ***MRI and Connectivity:***

### **MRI Data Collection (Baseline and Week 32).**

Before treatment begins and at the 6 month follow-up appointment (week 32), subjects will participate in an fMRI cue exposure session (Claus et al., 2011). Participants who are determined eligible to have an MRI scan will undergo a structural scan, using a Siemens 3T Trio, followed by a functional MRI scan that involves alcohol cue exposure. Our cue procedure is consistent with NIAAA guidelines and less risky than previous studies that have examined this mechanism in a sample receiving treatment (e.g., Myrick et al., 2008; Spagnolo et al., 2014; see protection of human subjects section). **Structural MRI (sMRI):** We will acquire a high-resolution protocol sufficient to permit accurate tissue classification and anatomical parcellation. For optimal contrast between gray matter (GM), white matter (WM) and cerebral spinal fluid (CSF) at 3T, we will use a multi-echo MPRAGE (MEMPR) sequence with the following parameters: TR/TE/TI = 2300/2.74/900 ms, flip angle = 8°, FOV = 256x256 mm, Slab thickness = 176 mm, Matrix = 256x256x176, Voxel size = 1x1x1 mm, Number of echos = 4, Pixel bandwidth = 650 Hz, Total scan time = 6 min. **Functional MRI (fMRI) – Cue-Elicited BOLD:** fMRI scans will be collected with single-shot full k-space echo-planar imaging (EPI) with ramp sampling correction using the intercommissural line (AC-PC) as a reference (TR: 2.0 s, TE: 27ms,  $\alpha$ : 70°, matrix size: 64 × 64, 32 slices, voxel size: 3 × 3 × 4 mm^3). Image-based higher order automatic shimming will be employed. FMRI data will be acquired with a 32-channel coil. Scanner instability and signal-to-noise ratio during fMRI scanning on a phantom will be monitored weekly throughout the project period. Automated analysis of scanner instability with the Weiskoff method is routinely performed. We have used our alcohol cue task successfully in over 600 individuals (Claus et al., 2011). It is reliable and well validated. The task compares the taste of an individual's favorite alcoholic beverage with a sweet, appetitive control taste (litchi juice). The task was designed to minimize movement by only administering 1 ml of each beverage through Teflon tubing that is attached to a computer controller gustometer, over each 24 second trial. It is important to note that the total amount of the alcoholic beverage is only 12 ml (less than a teaspoon). The task itself involves a block design with twelve pseudorandomly ordered alcohol and control trials that are presented in two consecutive runs. In order to examine whether the effects of MBRP differ from those of RP, we will calculate the signal change for alcohol minus the control condition in the precuneus, putamen, and anterior cingulate and use the signal in these regions of interest (ROIs) in the structural equation models (see analysis section).

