
### **Resting State Connectivity (Baseline and Week 32).**

Before treatment begins and at the 6 month follow-up appointment (week 32), a 10 minute resting state scan will be collected to derive measures of functional connectivity in the left and right executive control networks (LECN/RECN) following our previously published procedures (Weiland et al., 2014). These networks will be identified using functionally defined ROIs/nodes. The nodes for the LECN include: dorsolateral prefrontal cortex (DLPFC), left middle/superior frontal gyrus (MFG), left superior parietal gyrus/angular gyrus (PAR), left inferior/middle temporal gyri (TL), right crus I/crus II/Lobule VI (CE), and left thalamus (TH). The RECN nodes include: right DLPFC, right MFG, right PAR, right medial superior frontal gyrus (mSFG), left CE, and right caudate (CU). Functional connections between nodes, each pairwise correlation defined as an edge, will be calculated and used to create a correlation matrix between the time-series of all nodes within each network for each subject. A Fisher r-to-z transformation will be applied to r-values to yield z-scores. Connectivity strength as a primary global measure of connectivity for each network will be calculated as the mean of all pairwise

correlations between nodes within each network as well as other graph theory metrics (e.g., degree, efficiency, centrality). The framewise displacement (FD) for each subject will be calculated across the entire resting state run from the image motion parameter and used a covariate in the analyses.

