### **Specific Aim 3 - Mediational analyses.**

Mediational analyses based on structural equation modeling with latent variables will be used to examine the mechanisms by which MBRP has its effects on behavioral outcomes related to alcohol use and dependence (See Figure 4; HYPOTHESIS 4) (Baron & Kenny, 1986; [name] et al., 2007). Mediational analyses will utilize the methylation and inflammation data collected at 4 weeks, and changes in cue-elicited BOLD activation and network connectivity strength at 8 weeks as the mediators, and drinking outcome data collected at 20 weeks. The exogenous variable in the model is the contrast that compares MBRP to RP. Methylation, inflammation, and drinking outcomes are all conceptualized as latent variables, which means that they are not directly measured, but are rather inferred via the measurement of variables thought to be a consequence of the latent variable. Latent variables have advantages over measured variables in that they are more reliable and thus allow for higher power for the test of relationships between the underlying construct and other variables (Kline, 2010).

The model is then estimated in EQS, and both the fit of the model and the significance of the path coefficients are examined. If HYPOTHESIS 4 is supported, we will see significant paths from the treatment contrast to methylation and inflammation. Further, there will be significant paths from methylation to cue-elicited BOLD activation and from inflammation to network connectivity. Finally, we expect significant relationships between BOLD activation and network connectivity to drinking outcomes. Importantly, tests for the completeness of mediation of the treatment differences in drinking outcomes are employed through a one degree of freedom  $\chi^2$  test where a path directly from the treatment contrast to drinking outcomes is added to the model. A nonsignificant direct path and a nonsignificant change in  $\chi^2$  suggest that treatment effects on drinking outcomes were mediated through the series of molecular and brain-based mechanisms. A secondary test of mediation will utilize bootstrap methods to test the significance of, and confidence limits around, the mediated effect (Mackinnon & Dwyer, 1993). Similar mediational analyses have been widely used by Co-I [name] ([name] et al., 2007).

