### **Criteria for inclusion in the study are:**

1. Must be between the ages of *21 and 60* and provide informed consent;
2. Have a primary DSM-V diagnosis of alcohol use disorder;
3. Must be within 10 days of last drink;
4. Must have been drinking heavily (criteria dependent upon individual's age, gender, and BMI) for a consistent period of time;
5. Must have a breath alcohol level of 0 at screening (to sign consent form);
6. Not currently taking any medications for the treatment of psychiatric disorders, including substance use disorders, mood disorders, and psychosis;
7. Female subjects must not be pregnant, as indicated by a pregnancy test which will be administered at baseline (tests will be re-administered at the 32 week session prior to the MR scan);
8. Must not be positive for sedatives, opiates, cocaine, or amphetamine on drug screen at baseline;
9. Must not meet criteria for psychotic disorder, bipolar disorder, or a major depressive episode;
10. Must not have a Beck Depression Inventory (BDI) score of more than 28 (29-63 indicates severe depression);
11. Must not rate 2 or higher on BDI question 9 (assessment of suicidality);
12. Must have a Clinical Institute Withdrawal Assessment (CIWA) score less than 8 (indicating no need for medical detox). If CIWA is greater than 8, patient will be referred to detox and only accepted into study after detox is successfully completed.
13. Must have expressed a desire during their initial screen to reduce the number of drinks they regularly consume

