### **End of Treatment (8 weeks)**

At the end of treatment session, subjects will continue with their usual session with a therapist (including a BAC test), and either before or after their appointment, complete a set of follow-up outcome measures including questionnaires and neurocognitive tests, and provide a blood sample. Subjects will be compensated \$30 for completion of this session, plus an additional \$15 for completing each therapy session (weeks 1-3 and 5-7), for a total of \$90 if they have attended all 6 sessions. Participants will receive their second gut microbiome sample collection kits at the end of the session and will return them using a pre-paid, pre-addressed envelope that we will provide for them.

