### **Follow-up Assessment II (32 weeks) and MRI Scan II**

At this follow-up session, all subjects will take a BAC test, complete a set of self-report outcome measures and provide a blood sample. Subjects will be compensated \$50 for completing this

assessment (\$30 for completing self-report measures and \$20 for providing blood samples). For subjects who are unable to come into the laboratory, the option of completing self-report measures online (via Qualtrics) will be provided for a \$30 compensation. The same email will be sent for the second follow-up assessment as provided above.

All subjects who are eligible and selected to participate in the MRI scan portion of the study, will complete the second MRI scan during this appointment and receive an additional \$30 for completion of the second scan. Female participants will be asked to take a second pregnancy test free of charge and must have a negative result in order to go in the MRI. Following the MRI scan, a therapist will conduct an assessment with each participant after the cue exposure session to determine whether there is any residual craving or anxiety before leaving the session. Participants will also be provided with contact information for local AA and support groups for aftercare.

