**MRI/fMRI Scan Collected at Baseline and 8 weeks**

**MRI/fMRI In-task Measures**

- The MRI data collection will take place at the CU Boulder's INC MRI Suite in the CINC. We will utilize a 2011 3T research-only Siemens Trio system (Erlangen, Germany) with a 32-channel head coil, multinuclear support, clinical features (extremity coil, shoulder array coil, spectrus injector), and additional software (e.g., BLADE, inline diffusion/BOLD, spectroscopy, cardiac, advanced functional software). Scanner instability and quality control on a phantom will be monitored weekly. All participants will undergo a structural scan, followed by a functional MRI scan, which

---

includes the alcohol cue task.

Structural MRI (sMRI)	

For this sequence, participants will be asked to just lie still and stay awake. No other actions on their behalf are needed. We will collect high-resolution anatomical images to permit accurate tissue classification and anatomical parcellation. For optimal contrast between gray matter (GM), white matter (WM) and cerebral spinal fluid (CSF) at 3T, we will use a multi-echo MPRAGE (MEMPR) sequence with the following parameters: TR/TE/TI = 2300/2.74/900 ms, flip angle = 8°, FOV = 256x256 mm, Slab thickness = 176 mm, Matrix = 256x256x176, Voxel size =1x1x1 mm, Number of echos = 4, Pixel bandwidth =650 Hz, Total scan time = 6 min.

	6 minutes
Functional MRI (fMRI)	

fMRI scans will be collected with single-shot full k-space echo-planar imaging (EPI) with ramp sampling correction using the intercommissural line (AC-PC) as a reference (TR: 2.0 s, TE: 27ms, <math>\alpha</math>: 70°, matrix size: <math>64 \times 64</math>, 32 slices, voxel size: <math>3 \times 3 \times 4 \text{ mm}^3</math>). Image-based higher order automatic shimming will be employed. fMRI data will be acquired with a 32-channel coil. Scanner instability and signal-to-noise ratio during fMRI scanning on a phantom will be monitored weekly throughout the project period. Automated analysis of scanner instability with the Weiskoff method is routinely performed. We have used our alcohol cue task successfully in over 600 individuals (Claus et al.,

	6 minutes

---

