MBRP (or RP) Therapy Sessions (weeks 1-3 and 5-7)	
 
• BAC test; Mindfulness Relapse Prevention or Relapse Prevention therapy session with a trained therapist
 
	CINC	1 hour each session (6 hours total)
Intermediate Session (week 4)	
 
• BAC test; MBRP (or RP) therapy session; Questionnaires; Blood draw
 
	CINC	2 hours
End of Treatment Session (week 8)	
 
• BAC test; MBRP (or RP) therapy session; Questionnaires; Neurocognitive tests; Blood draw; receive microbiome kit
 
	CINC	2 hours
Mail-in Sample from Home	
 
• Subject will mail-in their collection kit back to our lab in a pre-paid, pre-addressed envelope.
 
	At Home	5 minutes

Follow-up Session (week 20)	
 
• BAC test; Questionnaires; Blood draw
 
	CINC	1 hour
Follow-up Session (week 32) & MRI Scan II	
 
• BAC test; Questionnaires; Blood draw; Pregnancy test; MRI scan
 
	CINC	1 hour (2 hours with scan)
Check-In Session (week 33)	
 
• BAC test; a check-in session with a therapist to discuss potential relapse.
 
	CINC	30 minutes
TOTAL TIME		Approximately 16 hours (18 hours with MRI)	

Due to the COVID-19 situation we are collecting remote data only and will return to our original protocol when it is safe to do so. The remote PROCEDURES will be as follows:

**BASELINE SESSION:** The first study appointment is an orientation and consent session, also referred to as the Baseline session. For this appointment, the participant will meet with a research assistant who will take them through the informed consent document and give them an opportunity to ask any questions about their participation in the study. The participant will show their ID over Zoom to the confirm they are between 21-60 years old. Then a research assistant will use Docusign to electronically sign the consent form and send it to the participant to sign. Signed consent forms will be stored securely on our server in a password protected folder.

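### Aim 3 needs a week-8 brain scan that no visit provides; the scheduled week-32 scan comes 12 weeks after the drinking outcome it is meant to explain

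*Combined protocol and SAP*

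**What the plan says.** The Data Analysis Plan (section IV, Specific Aim 3) sets out a time-ordered structural equation model: treatment, then methylation and inflammation at week 4, then "changes in cue-elicited BOLD activation and network connectivity strength at 8 weeks as the mediators, and drinking outcome data collected at 20 weeks". It expects significant paths from BOLD activation and connectivity to drinking.

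The rest of the protocol places the second scan elsewhere:

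- Section IV, MRI Data Collection: "Before treatment begins and at the 6 month follow-up appointment (week 32), subjects will participate in an fMRI cue exposure session".
- Section IV, Resting State Connectivity: "Before treatment begins and at the 6 month follow-up appointment (week 32), a 10 minute resting state scan will be collected".
- Inclusion criteria, on pregnancy testing: "tests will be re-administered at the 32 week session prior to the MR scan".
- Section XI, End of Treatment (8 weeks): participants "complete a set of follow-up outcome measures including questionnaires and neurocognitive tests, and provide a blood sample". No scan is listed.
- Section XI, Follow-up Assessment II: those "eligible and selected to participate in the MRI scan portion of the study, will complete the second MRI scan during this appointment".
- Section XI, visit table, week-32 row: "BAC test; Questionnaires; Blood draw; Pregnancy test; MRI scan". The week-8 row has no MRI.
- Section VIII attaches the second scan payment to week 32. The alcohol-exposure paragraphs in sections XV and XVI also put the second cue exposure at the second follow-up.

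One place agrees with the analysis plan, a heading in the instrument table of section XI: "MRI/fMRI Scan Collected at Baseline and 8 weeks".

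**The concern.** Mediation requires the mediator to change before the outcome. The Aim 3 text respects this (weeks 4, 8, 20), but the visits do not supply the middle step. The plan does not say what happens if only week-32 imaging exists. The obvious substitution would put the brain measure after the drinking it is supposed to explain.

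The stake is Hypothesis 4. One route runs from inflammation through network connectivity, the other from methylation through striatal cue response, and both must finish with a brain-to-drinking path. If imaging follows drinking, that path can be significant because drinking up to week 20 altered cue response or connectivity by week 32. Model fit, the one-degree-of-freedom test of the direct path and the bootstrap of the mediated effect cannot tell the two directions apart. If the mediator's timing is left open until data are in hand, the choice could also be made after seeing results.

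**Working it through.** **1. Timing.** Inputs: mediator week 8 and outcome week 20 (Specific Aim 3 analysis); second scan at week 32 (section IV, section XI and visit table).

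- Model as written: 20 − 8 = +12 weeks, so the mediator precedes the outcome.
- Scheduled scan: 20 − 32 = −12 weeks, so the mediator follows the outcome.
- Slip from the stated mediator time: 32 − 8 = 24 weeks.

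The Timeline Follow Back covers the prior 30 days (section XI), so the week-20 drinking window has closed 12 weeks before the scan. Using week-32 drinking instead does not restore the order: its recall window runs up to the scan visit, so mediator and outcome are at best concurrent.

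**2. Is a week-8 scan resourced anywhere?**

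- Payments (section VIII): 30 + 30 + 30 + 90 + 50 + 50 = $280 without scans. With two scans, 280 + 2 × 30 = $340, the stated maximum. The two scan payments are tied to baseline and week 32.
- Visit-table hours: 2.5 (baseline) + 1 (goal-setting) + 6 (therapy) + 2 (week 4) + 2 (week 8) + 0.08 (mailed sample) + 1 (week 20) + 1 (week 32) + 0.5 (week 33) = 16.08. Adding one hour for each of the two scans gives 18.08. The table states about 16 hours, and 18 with MRI.

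Both totals are used up by scans at baseline and week 32. Nothing is left for a week-8 scan.

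**3. Which links keep their order with a week-32 scan?** Treatment to week-4 markers: yes. Week-4 markers to week-32 imaging: yes. Treatment to imaging (Hypothesis 3): yes. Imaging to week-20 drinking: no.

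**4. How often could a reversed path look like mediation? (Illustration only.)** Suppose brain change has no effect on drinking, but week-20 drinking has a standardized effect r on week-32 imaging. The chance of a significant imaging–drinking association at two-sided alpha .05 is approximately Φ(atanh(r) × √(N − 3) − 1.96). The documents give neither r nor the number scanned, so both are assumed:

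| Assumed N scanned | r = .15 | r = .30 |
|---|---|---|
| 226 | .617 | .996 |
| 180 | .520 | .985 |
| 113 | .354 | .901 |

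For example, at N = 226 and r = .15: .1511 × √223 − 1.96 = 0.297, and Φ(0.297) = .617. The nominal rate is .05. The value r = .15 is close to d = .30 converted to a correlation (.30/√(.09 + 4) = .148). The value r = .30 reads the plan's .30 directly as a standardized path. The N values are everyone enrolled, the Aim 1 post-attrition total, and half of those enrolled.

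There is no stated figure to reproduce. The Aim 3 power values do not bear on the timing.

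**The case against.** The strongest reply has four parts.

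- **The week-8 scan is not absent from the document.** The instrument-table heading names it and agrees with the analysis plan, so this is an inconsistency rather than a badly chosen model. That stands as a description: the 4–8–20 order is sound in itself. It does not rescue the analysis, because no visit, payment or time allowance implements the heading.
- **The backwards mediator is hypothetical.** No text says week-32 imaging will be substituted, and week-32 drinking is also collected. The first point is right, and the harm is stated conditionally for that reason. The second only moves the problem from reversed to concurrent.
- **The percentages are soft.** They are the power to detect an assumed reverse association, computed for a simple correlation rather than the latent-variable model. The larger N values are optimistic: scanning is for those eligible and selected, participants may opt out, and no MRI is collected in the remote COVID-19 period. All of this stands. The figures show direction and scale, and the ordering argument does not need them.
- **The primary analysis is untouched.** Correct, and it bounds the point. Even so, a named specific aim cannot be run as written on the scheduled data.

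Figure 4, the path diagram, is not shown in the text available here. The conflict does not depend on it, because the timing is given in words.

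**Conclusion.** The concern holds and must be fixed before Aim 3 is analysed. The Aim 3 text and one table heading require imaging change at week 8; the operational schedule provides scans at baseline and week 32 only. On that schedule no visit supplies the stated brain mediator. The only scheduled substitute falls 12 weeks after the outcome and 24 weeks after the time the model states. These statements rest on the documents' own dates and need no assumptions.

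If week-32 imaging were used, a brain-to-drinking path could not support mediation. Under assumed reverse effects of .15 to .30 and assumed scanned samples of 113 to 226, it would be significant in roughly 35% to over 99% of trials with no true brain effect. The damage is confined to that link, but the link closes both routes of Hypothesis 4.

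**What to change.** Reconcile the Aim 3 analysis text and the instrument-table heading with the rest of the protocol, and state one time for the second scan.

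**If the scan is at week 32:**

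- test mediation of week-20 drinking only through week-4 methylation and inflammation;
- model week-32 imaging change as a downstream outcome of treatment and those markers;
- report any imaging–drinking relation as an association, including one with week-32 drinking;
- reword Hypothesis 4 and correct the table heading to match.

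This changes wording only and adds no scans or visits. Its price is that the full chain from molecular change through brain change to drinking can no longer be claimed.

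**If week 8 was intended:** keep the Aim 3 model. Bring the design headings, the repeat pregnancy test, the week-8 and week-32 visit descriptions, the visit table, compensation and the alcohol-exposure risk paragraphs into line. The week-33 check-in follows the week-32 cue exposure and must be reconciled too. This keeps the causal chain, but it moves or adds a scan, with visit, consent and budget changes, and cannot recover participants already past week 8.

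In either case, state the number of scanned participants expected to contribute to Aim 3, allowing for eligibility and selection, opt-out and the remote period. Fix the choice before outcome data are examined.

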### **Specific Aim 2.**

#### Examining the putative molecular mechanisms underlying the effects of MBRP versus RP.

- Hypothesis 2. Based on studies suggesting that MBIs alter epigenetic regulation of key genes implicated in alcohol dependence (i.e., DRD2, SLC6A3, DBH) and reduce inflammatory pathway activation (i.e., IL-8, IL-6, TNF $\alpha$ ), it is hypothesized that MBRP treatment will demonstrate significant decreases in methylation of key genes as well as decreases in inflammation biomarkers.
- Hypothesis 3. It is also hypothesized that individuals who receive MBRP, as compared to RP, will demonstrate greater LECN/RECN connectivity as well as reduced cue-elicited BOLD response in the striatum.

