### **Specific Aim 3.**

#### The third specific aim will determine whether the effectiveness of MBRP vs. RP on clinical outcomes is mediated by the effect of MBRP on molecular mechanisms, and, in turn, their effects on network connectivity and BOLD response.

- Hypothesis 4. It is hypothesized that the effects of MBRP on clinical outcomes (Hypothesis 1) will accrue through two routes: the effects of MBRP on reductions in inflammatory markers

(Hypothesis 2) which in turn influence LECN/RECN connectivity; and the effect of MBRP on methylation of key genes which in turn influence cue-elicited BOLD activation in the striatum (Hypothesis 3). These effects will be tested in the context of a structural equation modeling framework.

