### **DRD2 Methylation and BOLD Response to Alcohol Cues.**

BOLD response to alcohol cues in the nucleus accumbens and caudate were extracted from each individual in a previously collected data set ( $n=78$ ). Correlations between the BOLD response to alcohol cues in these structures and the average methylation of the 17 CpGs were calculated. Negative correlations were found between the average methylation of the 17 CpGs and the bilateral caudate (left:  $r = -0.273$ ,  $p = 0.027$ ; right:  $r = -0.305$ ,  $p = 0.013$ ) and nucleus accumbens (left:  $r = -0.247$ ,  $p = 0.045$ ; right:  $r = -0.241$ ,  $p = 0.052$ ).

[figure not shown]

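### The Hypothesis 4 criterion asks for significant paths without direction, while the sign of the methylation-to-BOLD link is open, so a route contrary to Hypotheses 2 and 3 could meet it as worded

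*Combined protocol and SAP*

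**What the plan says.** The only stated criterion for Hypothesis 4 is in the Data Analysis Plan, Specific Aim 3 - Mediational analyses. Model fit and the significance of the path coefficients are to be examined. If the hypothesis is supported, treatment will have significant paths to methylation and inflammation, "there will be significant paths from methylation to cue-elicited BOLD activation and from inflammation to network connectivity", and BOLD and connectivity will be significantly related to drinking. A nonsignificant direct path and a nonsignificant 1-df chi-square change are then said to "suggest that treatment effects on drinking outcomes were mediated through the series of molecular and brain-based mechanisms". The section adds: "A secondary test of mediation will utilize bootstrap methods to test the significance of, and confidence limits around, the mediated effect". None of these statements names a direction. The power section for Aim 3 uses two-tailed tests and unsigned effect sizes.

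Directions appear elsewhere:

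- **Hypothesis 2:** "it is hypothesized that MBRP treatment will demonstrate significant decreases in methylation of key genes".
- **Hypothesis 3:** under MBRP, greater connectivity and "reduced cue-elicited BOLD response in the striatum".
- **Hypothesis 4:** it cites Hypotheses 1 to 3 by number. For inflammation it speaks of "the effects of MBRP on reductions in inflammatory markers". For methylation it speaks only of "the effect of MBRP on methylation of key genes which in turn influence cue-elicited BOLD activation in the striatum".
- **Figure 1 legend (Background):** epigenetic modification sensitizes reward responding, and MBRP is meant to mitigate or reverse it.

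The direct evidence on methylation and BOLD is in Preliminary Studies: "Negative correlations were found between the average methylation of the 17 CpGs and the bilateral caudate", and likewise the accumbens.

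**The concern.** MBRP can lower BOLD by lowering methylation only if the methylation-to-BOLD path is positive. The protocol's own estimates of that link are negative. If the true path were negative, a fall in methylation would raise BOLD, contrary to Hypothesis 3, yet every path on the route could still be significant. The criterion as worded does not separate that result from the hypothesized one.

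The inflammation route has no such conflict. Its pilot correlations with connectivity (r = -.24 to -.55) agree with Hypotheses 2 and 3.

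What is at stake is the mechanistic conclusion of Aim 3. The primary comparison of heavy drinking days is not affected.

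**Working it through.** **1. Signs.** MBRP to methylation is negative (Hypothesis 2) and MBRP to BOLD is negative (Hypothesis 3). The effect through methylation is the product of MBRP-to-methylation and methylation-to-BOLD, so the second factor must be positive.

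**2. Direct data** (Preliminary Studies, DRD2, average of 17 CpGs):

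| Region | r | p |
|---|---|---|
| Left caudate | -.273 | .027 |
| Right caudate | -.305 | .013 |
| Left accumbens | -.247 | .045 |
| Right accumbens | -.241 | .052 |

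These p-values fit about 66 people better than the stated n=78 (n=66 gives .027, .013, .046 and .051). The signs do not change.

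**3. Indirect evidence is mixed.** DRD2 methylation rises with D2/D3 receptor availability (r = .650), which the Background says is low in dependence. Methylation also correlates negatively with AUDIT (-.276) and the Alcohol Dependence Scale (-.295). These count against the predicted direction. In its favour, the Background cites increased methylation in dependent patients in a number of genes, and Preliminary Studies links DRD2 methylation to less ability to control drinking over 12 weeks of treatment.

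**4. Size of a contrary route.** Use the d=.60 effect on methylation and on inflammation from the Aim 3 power section.

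- Rise in BOLD: .60 x .273 = .164 SD (.60 x .241 = .145 to .60 x .305 = .183).
- Other downstream paths: the power section states d=.30 but not its metric. Read as d or converted to r = .148, it gives power of about .61 to .62 at 226, not the stated .87. The three stated powers imply one common value: (1.96+.553)/sqrt(150) = .205; (1.96+.954)/sqrt(200) = .206; (1.96+1.126)/sqrt(226) = .205.
- Effect on drinking: methylation route .60 x .273 x .205 = +.034 SD; inflammation route -.60 x .205 x .205 = -.025 SD; net +.008 SD, so no benefit.

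**5. How often the criterion is met.** Simulated trials with 1:1 allocation, observed variables and complete data. Treatment lowers methylation and inflammation by .60 each. BOLD = b x methylation; connectivity = -c x inflammation; drinking = c x BOLD - c x connectivity + direct effect. Residual noise is added to each. The criterion requires all six paths at p<.05, and the added direct path and its 1-df likelihood-ratio test both at p>=.05.

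| b | c | Direct effect | N=226 | N=180 |
|---|---|---|---|---|
| -.273 | .205 | none | about 64% | about 46% |
| -.273 | .205 | d=.23 benefit | about 40% | about 31% |
| -.15 | .205 | none | about 40% | about 25% |
| -.273 | .15 | none | 24% | 14% |
| -.273 | .30 | none | 91-93% | 83-86% |

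N=180 is the completer count in the Aim 1 power section, and d=.23 is the smaller prior effect quoted there. At an assumed N=120 with b=-.273, c=.205 and no direct effect, the figure is about 17%.

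**6. With signs required.** The criterion is met in 0% of the b=-.273 cases, which is close to true by construction. With b=+.273 and c=.205, the signed and unsigned criteria are met equally often (about 64% and 45%), so requiring the sign costs no power.

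**7. Would Hypothesis 3 show it?** A one-region test finds a significant BOLD rise of .164 SD in only about 22% (N=226) or 19% (N=180) of trials. The Aim 2 power section gives d=.38 as the detectable effect.

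**The case against.** The strongest reply is that direction is already present. The section says what would be seen if Hypothesis 4 held, which is not formally a statement that significant paths establish it. Hypothesis 4 refers to the directional Hypotheses 1 to 3, and the Figure 1 legend conveys the intended direction. Figure 4, the path diagram, is missing from the file and may carry signs. Coefficients and bootstrap limits are signed, so a reversed path would be visible in the output. In the simulation, the criterion is almost never met together with a significant one-region BOLD reduction (under 0.1%), and seldom with a significant overall drinking benefit (about 0.5% with no direct effect, 1.8% with the d=.23 benefit).

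Much of this stands. A reader might infer that the plan has no directional hypothesis for this route, or that the true path is negative and a false confirmation is likely. The documents support neither. The pilot is cross-sectional and covers DRD2 alone, whereas the model uses latent methylation and change in BOLD. Caudate and accumbens are in the Hypothesis 3 outcome list but not among the regions that MRI Data Collection names for the structural model.

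What does not fall away is that this is the only criterion given, and it does not carry the direction over. Because the protocol's own pilot sign differs from the one its hypotheses imply, the sign cannot be taken as understood. Nor do Hypotheses 1 and 3 act as gates. The analysis plan keeps Aim 3 even if the arms do not differ on drinking, and Hypothesis 3 is weakly powered for effects of this size in either direction.

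**Conclusion.** The point holds as a gap in the stated criterion. Hypotheses 2 and 3 imply a positive methylation-to-BOLD path, the only direct data are negative, and the criterion accepts either sign. A methylation route that contradicts those hypotheses could therefore be reported as support for Hypothesis 4.

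The 64% and 46% are illustrations, not forecasts. They assume a true path of -.273, other paths of .205, d=.60 effects on both molecular markers, observed variables, no direct effect and complete blood and scan data. The rate falls with a separate benefit, a weaker path or fewer scans. The scanned number is not given: only eligible participants are scanned, and the remote phase collects neither MRI nor blood. The contrary effect on drinking is small, about .03 SD. Confidence is medium, and the change should be made because the mechanism is the purpose of Aim 3.

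**What to change.** In Specific Aim 3 - Mediational analyses:

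1. State the expected sign of each path and of each route's indirect effect. First reconcile Hypotheses 2 and 3 with the Figure 1 legend, the Background evidence on methylation and D2 receptors, and the DRD2 results in Preliminary Studies.
2. Base support for Hypothesis 4 on the already planned bootstrap interval, computed for each route's indirect effect. It must exclude zero in the hypothesized direction.
3. Use the nonsignificant direct path only as a completeness check, not as evidence of mediation.

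This takes a few sentences, with no new data and no new kind of analysis. When the hypothesized sign is true (b=+.273, c=.205), requiring both routes' intervals to lie on the side of benefit passes 68% of trials at N=226 and 49% at N=180, about the same as the present criterion. It passes 25% and 14% at c=.15, and 97% and 89% at c=.30. The downside is that a result of the opposite sign could no longer be called support for Hypothesis 4 and would be reported as contrary or exploratory.
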